### **Standard of Care Asthma Education:**

At each visit, the participant/parent will be contacted to cover the following topics and items:

- Education topics: basic facts of asthma, triggers, medication/inhaler technique
- Asthma Control Test (ACT) and other surveys
- Reduction strategies for identified asthma triggers

Title: Efficacy of Telemedicine Home Assessments for Identification and Reduction of

Asthma Triggers

PI: [name]

Institution: University of Arkansas for Medical Sciences (UAMS) and Arkansas Children's Hospital/Research Institute (ACH/ACRI)

Sponsor: UAMS Translation Research Institute (UAMS TRI)

### **Outcome Measures:**

Outcomes of patients receiving home assessments/interventions via TM will be compared to patients receiving standard of care trigger education. (**Table 1**) The **primary outcome** will be the mean difference in dust mite levels found in home dust samples at 4 months compared to baseline and between TM and standard of care groups. Other outcomes will be any change in the home environmental asthma trigger assessment score (heat) as a result of trigger mitigation performed at each home visit (TM group), changes in ACT score, comparison in number of exacerbations requiring a healthcare utilization or prescription for systemic steroids, and patient/household family retention of education provided during visits (both groups). We will measure study satisfaction among all participants and telemedicine-specific satisfaction among TM participants.

**Table 1. Summary of Outcome Measures**

	Baseline	2months	4months	6months
Dust Mite Levels	X		X	
Asthma Control Test (ACT)	X	X	X	X
Healthcare Utilization	X	X	X	X
Satisfaction Survey	X	X	X	X
Information Recall Survey		X	X	X

**Primary Outcome Measure:** The primary outcome measure will be the mean difference in dust mite levels found in home dust samples at 4 months compared to baseline and between TM and standard of care groups. Dust mites (*Dermatophagoides farina* and *Dermatophagoides pteronyssinus*) are one of the most common triggers for asthma and are commonly found throughout homes. ELISA testing can be utilized to quantify household dust mite levels with levels  $\geq 2$  mcg/g considered positive. Prolonged reductions in household dust mite concentrations are associated with improved asthma outcomes.

### **Secondary Outcome Measures:**

**Asthma Control Test (ACT):** The ACT is a validated 5-question ( $\geq 12$  years of age) or 7-question ( $<12$  years of age) survey used to assess asthma control. ACT is used for symptoms monitoring as per guidelines and has been identified as an appropriate asthma control composite score in clinical research.

**Healthcare Utilization:** At baseline, participants will be surveyed to determine the number of acute exacerbations he/she has experienced in the past 12 months resulting in hospitalization, emergency room/sick visits, or systemic steroid use. At each study time point, participants will record acute exacerbations resulting in hospitalization, emergency room or sick visits, or systemic steroid use since the previous asthma education session/TM home assessment visit.

**Visit Satisfaction:** We will administer ACH's outpatient satisfaction survey, supplied by National Research Corporation, at the completion of each visit for both groups. For TM

Title: Efficacy of Telemedicine Home Assessments for Identification and Reduction of

Asthma Triggers

PI: [name]

Institution: University of Arkansas for Medical Sciences (UAMS) and Arkansas Children's Hospital/Research Institute (ACH/ACRI)

Sponsor: UAMS Translation Research Institute (UAMS TRI)

participants, we will administer the telemedicine patient satisfaction survey that will ask respondents to assess four areas regarding the effectiveness and quality of care received via TM: 1) risk and benefits, 2) effectiveness, 3) efficiency, and 4) future adoption.

**Education Recall:** Participants and household parents/caregivers will be administered a questionnaire at each follow-up visit and again via phone call at 6 months to assess recall of education provided during each home assessment.

The ACT, healthcare utilization, visit satisfaction and education recall questionnaires will be completed via a mobile link and take approximately a total of 20 minutes to complete.

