**Inclusion Criteria:**

- 1) Age  $\geq 5$  years and  $\leq 18$  years
- 2) Have a diagnosis of persistent asthma as defined by national guidelines criteria
- 3) Patient receives care in ACH primary care, in patient and/or specialty clinics

Title: Efficacy of Telemedicine Home Assessments for Identification and Reduction of

Asthma Triggers

PI: [name]

Institution: University of Arkansas for Medical Sciences (UAMS) and Arkansas Children's Hospital/Research Institute (ACH/ACRI)

Sponsor: UAMS Translation Research Institute (UAMS TRI)

- 4) Patient has had at least one or more acute exacerbations of asthma within the 12 months prior to enrollment that led to an emergency department visit, hospital admission, or prescription for systemic steroids
- 5) English speaking participants/parents
- 6) Access to WIFI, smartphone or mobile device (tablet)

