Institution: University of Arkansas for Medical Sciences (UAMS) and Arkansas Children's Hospital/Research Institute (ACH/ACRI)

Sponsor: UAMS Translation Research Institute (UAMS TRI)

**Study Procedures, Outcome Measures, and Longitudinal Assessments:** For the proposed study, participants will receive home assessments for identification and reduction of asthma triggers via TM or standard of care asthma trigger education. Eligible subjects will undergo a total of 4 visits including an initial, in person screening/enrollment and initial demographic assessment visit, lasting approximately 1-2 hours. After enrollment and randomization, each TM participant will receive three home assessments including an initial baseline home assessment and two follow-up assessments, each 2 months apart (+/- two weeks). The home assessment visits will last approximately 90 minutes. During the TM home assessment, a home environmental asthma trigger assessment checklist (heat) will be utilized to identify potential asthma triggers in the subject's home. TM participants and their household will receive education and supplies, at the time of enrollment, for reduction of any identified triggers as well as education and supplies for general cleaning of the home. The Asthma Home Kit supplies provided to participants will include: Quickie 45TRI automatic sponge mop, child resistant roach and mice bait stations, zippered mattress covers, zippered pillow covers, trash can with lid, trash bags, anti-microbial sponges, rubber gloves, non-toxic all-purpose cleaner, Borax powder, scrubbing pads, Quickie home pro cleaning cloths, broom/dust pan, dusting spray, and paper towels. Each kit will contain labeled instructions on the proper use and/or storage of each item.

For those receiving standard of care education, each subject will receive the same education given to TM subjects for identification and reduction of asthma triggers, but will not receive TM home assessments or trigger reduction kits. Standard of care subjects will be contacted again at 2 months and 4 months (+/- 2 weeks) to assess retention of education materials and to provide additional asthma education and trigger reduction info. All participants will then receive a phone follow-up at 6 months (+/- two weeks) from the time of enrollment.

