### **Data Analysis**

#### **Sample size:**

*Analysis for the primary endpoint:* The primary outcome measure is level of dust mite allergens as measured by the MARIA™ test data. Using a one-way analysis of covariance, we estimated that a sample size of 20 in each of the two groups will yield at least 96% power to detect a 4  $\mu\text{g/g}$  difference between group means assuming a common standard deviation of 2 and a two-sided significance level of 5%.

Title: Efficacy of Telemedicine Home Assessments for Identification and Reduction of

Asthma Triggers

PI: [name]

Institution: University of Arkansas for Medical Sciences (UAMS) and Arkansas Children's Hospital/Research Institute (ACH/ACRI)

Sponsor: UAMS Translation Research Institute (UAMS TRI)

**Analysis for the secondary endpoint:** To evaluate the secondary outcome variables, the distribution for each outcome (i.e. home environmental asthma trigger score (heat), ACT score, healthcare utilization, visit satisfaction, and education recall) will be first assessed with summary statistics and graphical measures. It is anticipated that the distribution for some of these variables will be positively skewed. In cases of non-normal data, a logarithmic or square root transformation will be applied to normalize the distribution of the data. Secondary outcomes will be assessed for significant differences between groups and from baseline to 4 months and 6 months using a univariate repeated measure analysis of variance that will include a time x group interaction.

All tests will be two-sided and assume a significance level of 5%. All statistical analyses will be performed using SAS software version 9.4 (SAS Institute Inc., Cary NC, USA).

**Missing data and general considerations:** All reasons for drop out and missing data will be documented and reported. Subjects will be replaced if the dropout rate exceeds the estimate of 10%.

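### Healthcare utilization is counted over 12 months at baseline but about 2 months at each follow-up, so the planned test of change shows an 83% fall when nothing has changed

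*Combined protocol and SAP*

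**What the plan says.** Under Secondary Outcome Measures, the Healthcare Utilization paragraph sets the baseline measure: "At baseline, participants will be surveyed to determine the number of acute exacerbations he/she has experienced in the past 12 months". At every later time point the child's count covers only events "since the previous asthma education session/TM home assessment visit".

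Study Procedures, Outcome Measures, and Longitudinal Assessments spaces these contacts. The telemedicine (TM) arm has a baseline home assessment and "two follow-up assessments, each 2 months apart (+/- two weeks"). The standard-of-care arm is contacted at 2 and 4 months with the same tolerance. Both arms are called at 6 months, timed from enrolment.

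The secondary-endpoint paragraph of Data Analysis lists healthcare utilization by name. It states: "Secondary outcomes will be assessed for significant differences between groups and from baseline to 4 months and 6 months", using repeated-measures ANOVA with a time-by-group interaction. For skewed outcomes: "In cases of non-normal data, a logarithmic or square root transformation will be applied to normalize the distribution of the data".

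Inclusion criterion 4 also bears on the baseline count: "Patient has had at least one or more acute exacerbations of asthma within the 12 months prior to enrollment". The Outcome Measures section frames this outcome as a "comparison in number of exacerbations requiring a healthcare utilization or prescription for systemic steroids".

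**The concern.** The baseline and follow-up counts differ about six-fold in the time they cover, and nothing in the plan puts them on a common time base. A log or square-root transformation deals with skew, not with exposure. The planned test of change therefore measures mainly the difference in recall period. The entry rule adds to the apparent fall, because children are selected for having had an event in the baseline window.

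Specific Aim 2 is about changes in asthma morbidity. A time effect that is almost certain to be significant in both arms invites the false conclusion that utilization fell after enrolment.

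**Working it through.** The plan gives no event rate, effect size or power for this outcome, so there is no figure of its own to reproduce.

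**Inputs from the protocol.** Baseline window 12 months; follow-up window 2 months (1.5 to 2.5 with the two-week tolerance); 40 children randomized 1:1, so 20 per arm; two-sided 5% level; at least one exacerbation in the 12 months before entry.

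**Step 1: constant rate, no other assumption.** Expected count = rate x window, so the apparent fall is 1 - w/12 for a follow-up window of w months.

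- w = 2: 1 - 2/12 = 83.3%
- w = 1.5 and 2.5: 87.5% and 79.2%
- w = 1 and 3 (adjoining visits at opposite limits): 91.7% and 75.0%
- If counts were cumulated from baseline, which the text does not say: 1 - 4/12 = 66.7% at month 4 and 1 - 6/12 = 50.0% at month 6

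**Step 2: add the entry rule.** The documents give no rates, so these are assumed: mean m events a year, with gamma heterogeneity of variance h between children. Conditioning on a baseline count of at least 1, the null fall on a common time base is q = (1 + m·h)^(-1/h - 1). The raw 12-to-2-month fall is 1 - (1 - q)/6. For m = 1 and h = 0.5, q = 1.5^(-3) = 29.6% and the raw fall is 1 - 0.704/6 = 88.3%.

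| m per year | q at h = 0.3 / 0.5 / 1.0 | raw fall |
|---|---|---|
| 0.5 | 54.6 / 51.2 / 44.4% | 90.7-92.4% |
| 1 | 32.1 / 29.6 / 25.0% | 87.5-88.7% |
| 2 | 13.0 / 12.5 / 11.1% | 85.2-85.5% |
| 3 | 6.2 / 6.4 / 6.2% | 84.4% |

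Annualising the counts therefore removes the six-fold artefact but leaves q.

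**Step 3: rejection rates when nothing changes.** Simulation with 20 per arm, m = 1 to 3, h = 0.3 to 1.0, equal intervals in both arms, 4000 runs per cell, and 3 time points (baseline, 4, 6 months) or 4 (adding 2 months).

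- Time effect: 100.0% in every cell, on raw, log or square-root counts
- Group effect: 4.4-5.6%
- Time x group: log 4.1-5.6%; square root 4.1-5.4%; raw 5.4-8.8% uncorrected and 3.9-5.6% with Greenhouse-Geisser

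**Step 4: unequal intervals.** The protocol says "After enrollment and randomization, each TM participant will receive three home assessments including an initial baseline home assessment" but does not fix its delay after enrolment, whereas the 6-month call runs from enrolment. If the delay is d days, the last TM interval is 60.9 - d days. With d = 28 (assumed) it is 32.9 days against 60.9 in the other arm. If events before the first TM visit go uncounted, TM coverage is (182.6 - 28)/182.6 = 0.847 of the other arm's. With 3 time points, time x group on log counts then rejects in 7.1 / 9.4 / 11.8% of null trials at m = 1 / 2 / 3 (h = 0.5). At d = 14 it rejects in 5.2 / 5.9 / 6.5%.

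**Step 5: power for an assumed halving of the rate** (h = 0.5, 20 per arm, log counts in the first four rows):

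| Analysis | m = 1 | m = 2 | m = 3 |
|---|---|---|---|
| Time x group, 3 time points | 7.9% | 11.8% | 14.4% |
| Group effect, 3 time points | 11.0% | 14.5% | 17.5% |
| Group effect, 4 time points | 16.2% | 21.0% | 25.1% |
| ANCOVA of log(1 + 6-month total) on log baseline | 25.6% | 39.1% | 48.3% |
| Quasi-Poisson on 6-month total | 19.6% | 37.1% | 50.0% |

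**The case against.** The strongest reply is that Hypothesis 2 is comparative and the time-by-group term is its matching test. Both arms share the windows, so the artefact largely cancels between them. That stands, and it confines the defect to the time test. It depends on equal recall intervals and, for the interaction, on a transformation or a Greenhouse-Geisser correction. The plan already expects skew and prescribes a transformation, so the raw-count problem is the less likely path. The delay to the first TM visit is an assumed input; only the lack of a fixed date comes from the protocol.

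A second reply is that the analysis sentence is a blanket statement over five outcomes and cannot apply literally to all of them: education recall has no baseline in Table 1. The scale for utilization might have been settled later. But utilization is named and does have a baseline, and no passage supplies a rate.

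Third, the entry rule and the outcome do not count quite the same events, since the outcome also includes sick visits. This is correct and makes matters worse: if half of the counted events are of the qualifying type (assumed, h = 0.5), the null fall after annualising is 34 / 17 / 10% at 1 / 2 / 3 events a year, against 30 / 12.5 / 6% in Step 2.

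Finally, one sentence barring interpretation of the time effect would remove the error itself. That is true; moving to the 6-month total goes further, for the sake of power.

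**Conclusion.** The concern holds. Followed as written, the baseline-to-follow-up test for healthcare utilization is not interpretable. The 83% fall at a constant rate rests only on the protocol's own windows (79-88% for intervals of 1.5 to 2.5 months). The near-certain significance, the 84-89% fall with the entry rule at 1 to 3 events a year, and the 6-32% left after annualising rest on assumed rates and heterogeneity.

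The comparison between arms remains usable under the stated conditions, but the planned tests are weaker than a comparison of 6-month totals. This is one secondary outcome in a 40-child pilot, and the primary endpoint is untouched. It should be fixed before analysis but does not threaten the trial.

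**What to change.** Take healthcare utilization out of the baseline-to-follow-up ANOVA. Suggested text:

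> The total number of acute exacerbations from enrolment to the 6-month contact will be compared between arms, with the log of the 12-month baseline count as covariate. The between-arm estimate will be reported with its 95% confidence interval. Change from the baseline count will be neither tested nor interpreted. In both arms the first recall interval starts at enrolment, and the start and end dates of each interval are recorded.

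Name one model in advance: a count model with log(days observed) as offset, or an ANCOVA of log(1 + total). Their power is similar. The count model also accommodates unequal or incomplete follow-up, which the Participant Withdrawal section says will be analysed; the ANCOVA needs equal coverage. State how a reported baseline of zero is resolved, since it conflicts with eligibility and its log is undefined. The health-record access already covered by consent can be used to check reported counts over the same dates.

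**Cost.** Analysis wording, interval dates, and a question on events between enrolment and the first TM home visit; no extra contacts. As a protocol amendment it needs IRB approval, and Aim 2's reference to changes should be read as a difference between arms for this outcome. The result becomes a rate ratio or log-scale difference instead of a mean change. Power stays limited: about 20-26%, 37-39% and 48-50% for a halved rate at 1, 2 and 3 events a year. The count model is somewhat conservative when events are few (null rejection 3.3-4.7% at 1 to 3 a year, 1.8-2.7% at 0.5 a year).

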**Exclusion Criteria:**

- 1) Age <5 or >18 years
- 2) Non-English speaking participants/parents
- 3) Patients not receiving primary and/or asthma specialty care or inpatient services at ACH
- 4) Inability of patient or family to participate in TM evaluation due to lack of access to WiFi or smartphone or mobile device

***Rationale for only enrolling participants with persistent asthma:*** Only children with persistent asthma will be recruited to participate in the proposed study because they require regularly scheduled, follow-up to monitor asthma control and prevention of future exacerbations. Patients with intermittent asthma will not be recruited for participation because they typically are not at high risk of acute exacerbation nor require specialty care.

**Recruitment:** Potential participants will be recruited from ACH primary care or asthma subspecialty clinics through direct patient contact and advertising. These patients may also receive care in other ACH settings such as the emergency department, inpatient services or may be registered in institutional research participant databases, so we will recruit from these locations if needed to meet recruitment goals. Only one child per household who meets eligibility criteria will be enrolled.

We will utilize flyers, ACH/ACRI Intertube, and electronic signage to advertise the study. We will advertise via ACH/ACRI social media (i.e. Facebook, Twitter, and YouTube). The study will also be advertised via word of mouth. The advertisements will provide the contact information allowing parents/caregivers/potential adult participants to directly contact research staff. The clinics will be provided the study coordinator/respiratory therapist contact information to address any questions.

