**Randomization:** Subjects will be randomized 1:1 into 2 groups. One group will receive TM home assessments/interventions for identification and reduction of asthma triggers in the home while the other group will receive standard of care asthma trigger education. Randomization will occur at the time of enrollment visit after consent and assent is obtained and initial demographic assessment is complete. All participants will receive the same asthma education and trigger reduction materials. For those randomized to TM, participants will receive TM assessment of their home as well as an Asthma Home-Assessment kit that will provide supplies to reduce asthma triggers in the home.

**The Role, Qualifications, and Expectations of the Home Visitor (HV):** The Home visitor (HV) is a frontline public health worker who is a trusted member of and/or has an unusually close understanding of the community served. The HV is in a unique position to partner with families due to living in the area they are serving or having similar cultural backgrounds. The person acting in this role will be responsible for performing standard of care trigger education and asthma TM home assessments to aide in the identification and reduction of exposure to indoor asthma triggers. The goal is to establish a trusting partnership with participants and family members by providing education and tools to maximize asthma control and management as well as model appropriate behavior standards and core values as exemplified by Arkansas Children's mission and vision statement. For the purpose of this pilot project, the HV will enter into a contract agreement with UAMS or the Arkansas Children's Research Institute (ACRI) for the period of the pilot project. A minimum of a high school education, with a Bachelor degree in a health or social science related field preferred. In addition, one year of experience in some type of home visiting related to health care. Asthma specific training will be provided in the amount of 10 hours by a Certified Asthma Educator. The HV will receive CITI training as well. The education materials are provided by the Association of Asthma Educators and a certificate of completion is awarded after post testing. The HV will be expected to carry out the asthma home assessment via TM consistent with the procedures listed below.

Title: Efficacy of Telemedicine Home Assessments for Identification and Reduction of

Asthma Triggers

PI: [name]

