### **Ethical Considerations**

This study will be conducted in accordance with all applicable government regulations and UAMS research policies and procedures. This protocol and any amendments will be submitted and approved by the UAMS Institutional Review Board to conduct the study.

At the time of the detailed screening, the parent/caregiver/adult participant will indicate "Yes" on the eligibility document acknowledging verbal consent to complete the eligibility screener. The formal consent of each subject, using the IRB-approved consent form, will be obtained before the participant is submitted to any study procedures. All participants for this study will be provided a consent form describing the study and providing sufficient information in language suitable for participant to make an informed decision about their participation in this study. The person obtaining consent will thoroughly explain each element of the document and outline the risks and benefits, alternate treatment(s), and requirements of the study.

The consent process will take place in a quiet, private room and participants may take as much time as needed to make a decision about their participation. Participant privacy will be maintained and questions regarding study participation will be answered. No coercion or undue influence will be used in the consent process. Assent will be obtained from capable participants 7-17 years of age. This consent form must be signed by the participant or legally authorized representative, and the individual obtaining the consent. A copy of the signed consent will be given to the participant, and the informed consent process will be documented in each participant's research record.

**CONFIDENTIALITY:** The participant's records will be kept confidential with the exception of the Office for Human Research Protection (OHRP), UAMS IRB and other institutional oversight offices. The participant will be made aware that the Investigator

Title: Efficacy of Telemedicine Home Assessments for Identification and Reduction of  
Asthma Triggers

PI: [name]

Institution: University of Arkansas for Medical Sciences (UAMS) and Arkansas Children's Hospital/Research Institute  
(ACH/ACRI)

Sponsor: UAMS Translation Research Institute (UAMS TRI)

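### The education-recall analysis leaves age, known before randomisation, in the error of the arm comparison; this costs precision but does not bias the test

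*Combined protocol and SAP*

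**What the plan says.** - **Who is asked.** Secondary Outcome Measures, Education Recall: "Participants and household parents/caregivers will be administered a questionnaire at each follow-up visit", with a further phone administration at 6 months. The eligible ages are 5 to 18; the first exclusion criterion reads "Age <5 or >18 years". The paragraph does not say whether child and caregiver answer separately or together. The Outcome Measures section describes the outcome as "patient/household family retention of education provided during visits (both groups").
- **When.** Table 1 marks information recall at 2, 4 and 6 months, and not at baseline.
- **How it is analysed.** Data Analysis, secondary endpoint, lists recall once, in the series "ACT score, healthcare utilization, visit satisfaction, and education recall". The planned comparisons are "significant differences between groups and from baseline to 4 months and 6 months". The same sentence names one method for all of these outcomes, to be tested "using a univariate repeated measure analysis of variance that will include a time x group interaction". No age, respondent or household term is named.
- **What is known beforehand.** Pre-screening captures age. The Randomization paragraph says "Randomization will occur at the time of enrollment visit after consent and assent is obtained and initial demographic assessment is complete". Allocation is 1:1, with no stratification by age stated.

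**The concern.** How much taught material a child can repeat back plausibly depends on age, and the trial spans ages 5 to 18. The plan itself uses different ACT forms below and above age 12, but describes no such split for recall.

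With no baseline recall score, change from baseline cannot be computed for this outcome, and no baseline score is available to absorb stable differences between children. The main usable contrast is the difference between arms at follow-up, which is tested against between-subject variation. Age-related variation sits there unless it is modelled.

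At stake is the precision of one secondary result. Retention of education is among the claims in the overarching hypothesis, though in neither Specific Aim, and the trial has 20 children per arm.

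**Working it through.** **Inputs from the documents:** 20 per arm, two-sided 5% level, ages 5 to 18, recall at 2, 4 and 6 months. **Not given:** the SD of recall, a target difference, and the relation of recall to age. The plan states no power for recall; its 96% figure concerns dust mite level and has no bearing here. I therefore assume a difference of d = 0.7 SD and let age explain a share R² of the within-arm variance of child recall, from 5% to 50%.

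**1. Standard error of the arm difference, in SD units.** Unadjusted: √(2/20) = 0.316. Adjusted: 0.316 × √(1 − R²). The relative reduction is 1 − √(1 − R²), and the equivalent gain in children is 1/(1 − R²) − 1.

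**2. Power.** Noncentral t with noncentrality d/√(1 − R²) × √(20/2). Unadjusted: 0.7 × 3.162 = 2.214 on 38 df, power 57.8%. The age term leaves 37 df.

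| R² (assumed) | SE | SE reduction | Equivalent extra children | Noncentrality | Power |
|---|---|---|---|---|---|
| 0, unadjusted | 0.316 | – | – | 2.214 | 58% |
| 5% | 0.308 | 3% | 5% | 2.271 | 60% |
| 10% | 0.300 | 5% | 11% | 2.333 | 62% |
| 20% | 0.283 | 11% | 25% | 2.475 | 67% |
| 50% | 0.224 | 29% | 100% | 3.130 | 86% |

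If age explained nothing, the lost degree of freedom would leave power at 57.8%, the same to one decimal. The calculation is for one visit. It also holds for the mean of the three visits, with the SD and R² defined for that mean.

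**3. Does omitting age distort the test?** In 5,000 simulated trials with ages uniform over 5 to 18 and no arm effect, the unadjusted test rejected 5.2% (R² 20%) and 5.0% (R² 40%) of the time. The adjusted test rejected 4.8% and 5.1%. The nominal level holds either way.

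**4. If both answers in a household were entered as independent rows.** Let ρ be the within-household correlation and D the child–caregiver gap in SD. The true variance of an arm mean is (1 + ρ)/(2n). The variance the naive test uses is about (1 + D²/4)/(2n). Their ratio is (1 + ρ)/(1 + D²/4).

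| ρ | D | Ratio | Simulated rejection under no effect (nominal 5%) |
|---|---|---|---|
| 0.3 | 0 | 1.30 | 9.0% |
| 0.5 | 0 | 1.50 | 10.9% |
| 0.3 | 1 | 1.04 | 5.4% |
| 0.5 | 1 | 1.20 | 7.2% |

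At D = 1.5 the ratio falls to 0.83 (ρ = 0.3) or 0.96 (ρ = 0.5), and rejection is about 3–5%. Averaging within household before testing restored about 5% in every case simulated, with D at 0 or 1.

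**The case against.** The strongest reply is that an unadjusted randomised comparison is valid, that recall is an unpowered secondary outcome of a pilot, and that every R² above is assumed. All of that stands. At R² of 5–10% the gain is small, and for a joint household answer the child's age may matter little. Stable age differences also cancel from the within-subject time and time-by-group tests. What remains is the comparison of arm levels, where an already collected covariate could reduce the error at almost no cost.

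A reader might infer more than the documents support:

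- *That child and caregiver scores are pooled as separate observations, inflating the false-positive rate.* The plan does not say so. The household wording in Outcome Measures allows a single joint answer. The 9–11% figure also needs a zero gap between child and caregiver, which sits badly with the view that they differ.
- *That the model contains time and group and nothing else.* The text says what the ANOVA will include; it does not rule out other terms.
- *That a chance age imbalance between arms biases the result.* The randomised test already allows for such imbalance, as step 3 shows.
- *That the youngest children cannot answer.* The Ethical Considerations sentence, "Assent will be obtained from capable participants 7-17 years of age", concerns assent. It says nothing about ability to complete a questionnaire.
- *That one caregiver must be the sole tested respondent.* That would narrow an outcome that the plan defines for patient and household.

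**Conclusion.** The point holds as a modest loss of precision. No age term is named for recall, no baseline recall exists to do the same work, and age is available before randomisation. Adjustment cuts the standard error by about 3–5% if age explains 5–10% of the variance, and by 11–29% if it explains 20–50%. Power for a 0.7 SD difference with 20 per arm then moves from 58% to 60–62% or to 67–86%. These figures rest on the assumed difference and R², on a roughly linear age effect, and on scores given by the child; the documents cannot say where in the range the trial lies. Inflated type I error is conditional on both answers being entered as independent rows, which the plan does not state.

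**What to change.** In the secondary-endpoint paragraph of Data Analysis, add age at enrolment as a prespecified covariate in the recall model for scores given by the child. Record on the form who answered at each visit. If child and caregiver scores are both analysed, either report them separately or model them together with a respondent term and a household random effect.

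The cost is a sentence or two in the plan, one field on the form, and one degree of freedom for age. Reporting the two scores separately also adds a test, so the plan should say how the two results will be read together.
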